6.3 Angiographic Core Laboratory

Angiographic results will be submitted to an independent Core Laboratory for review and quantification of angiographic parameters (Beth Israel Deaconess Medical Center Imaging Laboratory, Boston, MA).

6.4 Clinical Events Adjudication

All clinical end-points are to be adjudicated by an independent clinical events committee using definitions consistent with the investigational plan. The CEC will develop a prospective CEC charter before any study data is adjudicated.

7 Adverse Events

An AE is defined as any untoward medical occurrence, unintended disease or injury, or untoward clinical signs (including abnormal laboratory findings) in subjects, users, or other persons, whether or not related to the investigational medical device.

Any pre-existing condition known to the investigator will not, in general, be reportable as an AE, unless the investigator believes that the participation of the subject in this study contributed to the progression of that condition.

When an AE has, by its nature, a prolonged course, the event will be considered a single event and not multiple events.

Death itself should not be recorded as an AE, but should only be reflected as an outcome of another specific AE. Any AE experienced by the study subjects after enrollment and up until index procedure hospital discharge must be recorded in the CRF.

7.1 Serious Adverse Events

Any AE that:

- Led to death

- Led to a serious deterioration in the health of the subject that resulted in
 - Life-threatening illness or injury or
 - Permanent impairment of a body structure or a body function or
 - In-patient hospitalization or prolongation of existing hospitalization.
 - Medical or surgical intervention to prevent permanent impairment of a body structure or a body function
 - Led to fetal distress, fetal death, or a congenital abnormality or birth defect
 - The following hospitalizations are not considered AEs/SAEs:
 - Planned hospitalizations for a pre-existing condition.

7.2 Anticipated Adverse Device Effects

A serious adverse device effect (ADE) that by its nature, incidence, severity or outcome has been previously identified as noted in the protocol risks section, 2.3 or the device IFU.

7.3 Unanticipated Adverse Device Effects

Per United States Code of Federal Regulations (CFR) Title 21, Part 812.3, an unanticipated ADE (UADE) is any serious adverse effect on health or safety or any life-threatening problem or death caused by or associated with a device, if that effect, problem, or death was not previously identified in nature, severity, or degree of incidence in the investigational plan or application (including a supplementary plan or application) or any other unanticipated serious problem associated with a device that relates to the rights, safety, or welfare of subjects.

8 Device Failure and Device Malfunction

A device has failed or malfunctioned if it is used in accordance with the IFU/IB but does not perform according to the IFU/IB and negatively impacts the treatment.

Device deficiencies and other device issues should not be reported as AEs. Instead, they should be reported on the appropriate CRF per the study CRF Completion Guidelines. If an AE results from a device deficiency or other device issue, the AE should be reported on the appropriate CRF.

9 Statistics

This study is designed as a single-arm observational trial. The study sample size is based upon treatment of a reasonable number of subjects with the study device to provide a reliable and meaningful assessment of device performance, rather than based upon any statistical hypothesis of an endpoint.

All statistical analyses will be performed on an intent-to-treat basis. The baseline demographic and lesion characteristics and angiographic and clinical outcomes will be evaluated by descriptive statistics. These calculations will be performed under the assumption that the data are in a normal distribution. All enrolled subjects will be analyzed on an intent-to-treat (ITT) basis as well as per protocol criteria.

10 Direct Access to Source Data/Documents

- 10.1 The Investigator and the associated institution will permit direct access to source data/documents for study-related monitoring, audits, IRB review and regulatory inspections.
- 10.2 Subjects providing informed consent agree to allow Sponsor or designee access and copying rights to pertinent information in their medical records concerning their participation in this study. The Investigator will obtain, as part of the informed consent, permission for study monitors or regulatory authorities to review in confidence any records identifying the subjects in this study. This information may be shared with regulatory agencies; however, the Sponsor undertakes not to otherwise release the patient's personal and private information.

11 Quality Control and Quality Assurance

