### 7.2 Summary of Study Data

The baseline demographic and lesion characteristics and angiographic and clinical outcomes will be evaluated by descriptive statistics. These calculations will be performed under the assumption that the data are in a normal distribution. All continuous variables will be summarised using the following descriptive statistics: n (non-missing sample size), mean and standard deviation. The frequency and percentages (based on the non-missing sample size) of observed levels will be reported for all categorical measures. Deaths, Serious Adverse Events and other Significant Adverse Events will be reported as number and percentage. All analyses will be performed using SAS version 9.4 (NC, USA).

---

Lesion related outcomes were assessed using core lab data. Where core lab was not analyzable, site reported data were used. No outcomes were imputed.

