### Table Listings

Number	Table Title	Summary Statistics
1	Primary end-point	n (%)
2	Secondary end-points	n (%)
3	Summary of baseline patient characteristics	n, mean, SD, Median, min, max, n (%)
4	Summary of discharge patient data	n, mean, SD, Median, min, max, n (%)
5	Summary of procedural patient characteristics	n, mean, SD, Median, min, max, n (%)
6	Summary of site reported lesion level Data	n, mean, SD, Median, min, max, n (%)
7	Core lab lesion level data	n, mean, SD, Median, min, max, n (%)
8	Lesion level study outcomes	n, mean, SD, Median, min, max, n (%)
9	In-hospital patient level outcomes	n (%)

Table 1: Primary End-Point:

	Overall population N = patients
Primary Endpoint	
Successful balloon delivery to the target lesion	
No	
Yes	
Successful inflation at the target lesion	
No	
Yes	
Successful deflation and withdrawal of the study balloon	
No	
Yes	
Vessel Perforation	
No	
Yes	
Flow limiting dissection (Grade C or Higher)	
No	
Yes	
No reduction in TIMI flow from baseline related to the study balloon (i.e. TIMI>=0)	
No	
Yes	
Final TIMI flow grade of 3 at the conclusion of the PCI procedure	
No	
Yes	

Table 2: Secondary End-Points:

	Overall population N = patients
Successful balloon delivery to the target lesion	
No	
Yes	
Successful inflation at the target lesion	
No	
Yes	
Successful deflation and withdrawal of the study balloon	
No	
Yes	
Vessel Perforation	
No	
Yes	
Flow limiting dissection (Grade C or Higher)	
No	
Yes	
No reduction in TIMI flow from baseline related to the study balloon (i.e. TIMI $\geq$ 0)	
No	
Yes	
Final TIMI flow grade of 3 at the conclusion of the PCI procedure	
No	
Yes	
Balloon rupture of the study balloon	
No	
Yes	
Improvement in Minimum Lumen Diameter	
No	
Yes	
Lesion success	
No	
Yes	
Vessel Perforation	
No	
Flow limiting dissection (Grade C or Higher)	
No	
Yes	
No reduction in TIMI flow from baseline related to the study balloon (i.e. TIMI $\geq$ 0)	
No	
Yes	

	Overall population N = patients
Clinically Significant Arrhythmia	
No	
Yes	

Table 3: Baseline patient characteristics:

	Overall population N = patients
CLINICAL CHARACTERISTICS	
Age (Years)	
N, N Missing	
Mean ± Std	
Min , Max	
Median (IQR)	
Gender	
Female	
Male	
Race	
Asian	
Black	
White	
BMI (kg/m  )	
N, N Missing	
Mean ± Std	
Min , Max	
Median (IQR)	
Diabetes Mellitus	
No	
Yes	
Diabetes Treatment	
Diet	
Insulin	
None	
Oral Medication	
Current Cigarette smoking (within 30 days)	
No	
Yes	
Hypercholesterolemia (requiring treatment)	
No	
Yes	

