Patient required new hemodialysis post-PCI	
Missing	
No	
POST PCI ECG	
12-lead electrocardiogram performed	
No	
Yes	
Rhythm	
AF/flutter	
Other	
Sinus Rhythm	
Q wave	
No	
Yes - Existing	
ST-segment depression or elevation	
No	
Yes - Existing	
POST PCI MEDICATIONS	
ACE inhibitors or ARB	
No	
Yes	
Beta-blockers	
No	
Yes	
Calcium channel blockers	
No	
Yes	
Long-acting nitrate	
No	
Yes	
Ranexa	
No	
Yes	
Oral Anticoagulation	
No	
Yes	
Statins	
No	
Yes	

	Overall population N = patients
Proton pump inhibitor	
No	
Yes	
Aspirin	
No	
Yes	
P2Y12 inhibitor	
Clopidogrel	
None	
Prasugrel	
Ticagrelor	

Table 5: Procedural patient characteristics

	Overall population N = patients
PROCEDURAL CHARACTERISTICS	
Number of lesions per patients	
Multiple	
Single	
Extent of coronary artery disease (number of vessels with CAD >= 50%)	
1	
2	
3	
Presence of Left main disease >= 50%	
No	
Yes	
Total contrast volume used (diagnostic and intervention) (ml)	
N, N Missing	
Mean ± Std	
Min , Max	
Median (IQR)	
Procedure duration (min)	
N, N Missing	
Mean ± Std	
Min , Max	
Median (IQR)	
Total fluroscopy time (min)	
N, N Missing	
Mean ± Std	
Min , Max	
Median (IQR)	
Specify arterial sheath access	
Femoral	
Radial	
Procedural medication (within 72 hours of PCI)	
Bivalirudin	
Low molecular weight heparin	
Unfractionated heparin	
Heart rate(beats per min)	
N, N Missing	
Mean ± Std	
Min , Max	
Median (IQR)	

	Overall population N = patients
Systolic Blood Pressure(mmHg)	
N, N Missing	
Mean ± Std	
Min , Max	
Median (IQR)	
Diastolic Blood Pressure(mmHg)	
N, N Missing	
Mean ± Std	
Min , Max	
Median (IQR)	

Table 6: Lesion level data (Site reported)

	Overall population N = lesions
LESION CHARACTERISTICS	
SAPPHIRE II PRO Device size	
1.0 x 10 mm	
1.0 x 15 mm	
1.0 x 8 mm	
1.25 x 10 mm	
1.25 x 15 mm	
1.25 x 5 mm	
1.25 x 8 mm	
Vessel treated	
Bypass graft	
Diagonal branch of LAD	
LAD	
LCx	
Marginal branch of LCx	
Posterior descending branch of RCA	
RCA	
Lesion location	
Distal	
Mid	
Ostial	
Prox	
Number of inflations per lesion	
0	
1	
2	
3	
Successful balloon delivery to the target lesion	
Yes	
Successful balloon inflation and deflation at the target lesion	
No	
Yes	
Inflation pressure (atm)	
N, N Missing	
Mean ± Std	
Min , Max	
Median (IQR)	
Number of inflations per lesion	
01	

	Overall population N = lesions
02	
03	
04	
05	
06	
Was there balloon rupture?	
No	
Yes	
Successful withdrawal of the balloon from the target lesion	
Yes	

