Was any post-dilation performed with stent implantation?	
No	
Not applicable	
Yes	
Was post procedural TIMI flow <3 at any lesion?	
No	
Yes	
Stent type implanted	
Biodegradable polymer stent (eg. Synergy)	
None	
Other	
Resolute	
Xience	
Stent implanted	
No	
Yes	

Table 7: Core lab lesion level data

	Overall population N = lesions
CASS Segment	
N, N Missing	
Mean ± Std	
Min , Max	
Median (IQR)	
CORE LAB	
Lesion location	
Missing	
Distal	
Mid	
Ostial	
Prox	
Lesion Length analyzable	
Missing	
No	
Lesion length (mm)	
N, N Missing	
Mean ± Std	
Min , Max	
Median (IQR)	
Eccentricity	
Missing	
Concentric	
Eccentric	
Thrombus	
Missing	
No	
Yes	
Tortuosity	
Missing	
None	
Calcification	
Missing	
Mod	
None	
Not-analyzable	
Severe	
Ulceration	
Missing	

	Overall population N = lesions
No	
Yes	
Aneurysm	
Missing	
No	
Intimal Flap	
Missing	
No	
Pre TIMI	
Missing	
0	
1	
2	
3	
Number of frames	
N, N Missing	
Mean ± Std	
Min , Max	
Median (IQR)	
Bifurcation	
Missing	
No	
Yes	
Prox Main branch	
Missing	
No	
Not-analyzable	
Yes	
Distal Main branch	
Missing	
No	
Not-analyzable	
Yes	
Side branch	
Missing	
No	
Not-analyzable	
Yes	
Branch diameter stenosis analyzable	
Missing	
No	

	Overall population N = lesions
Yes	
Branch diameter stenosis, %	
N, N Missing	
Mean ± Std	
Min , Max	
Median (IQR)	
Prox Normal analyzable	
Missing	
No	
Prox Normal(mm)	
N, N Missing	
Mean ± Std	
Min , Max	
Median (IQR)	
Distal Normal analyzable	
Missing	
No	
Distal Normal(mm)	
N, N Missing	
Mean ± Std	
Min , Max	
Median (IQR)	
MLD analyzable	
Missing	
No	
MLD(mm)	
N, N Missing	
Mean ± Std	
Min , Max	
Median (IQR)	
Prox Normal analyzable	
Missing	
No	
Yes	
Prox Normal(mm)	
N, N Missing	
Mean ± Std	
Min , Max	
Median (IQR)	
Distal Normal analyzable	
Missing	

	Overall population N = lesions
No	
Yes	
Distal Normal(mm)	
N, N Missing	
Mean ± Std	
Min , Max	
Median (IQR)	
MLD analyzable	
Missing	
No	
Yes	
MLD(mm)	
N, N Missing	
Mean ± Std	
Min , Max	
Median (IQR)	
CORONARY DILATATION CATHETER	
Aneurysm	
Missing	
No	
Not-analyzable	
Post TIMI	
1	
2	
3	
Number of frames analyzable	
Missing	
No	
Yes	
Number of frames	
N, N Missing	
Mean ± Std	
Min , Max	
Median (IQR)	
No Reflow	
Missing	
No	
Not-analyzable	
Abrupt closure	
Missing	
No	

	Overall population N = lesions
Not-analyzable	
Dissection	
0	
Staining	
Missing	
Not-analyzable	
Dissection Length analyzable	
Missing	
No	
Dissection Length (mm)	
N, N Missing	
Mean ± Std	
Min , Max	
Median (IQR)	
Branch % stenosis analyzable	
Missing	
No	

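### SAP mock Table 7 summarises the core-lab CASS Segment, apparently an anatomical code, by mean, SD and median instead of counts per segment

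*Protocol*

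**What the plan says.** Protocol section 9 (Statistics) sets out a descriptive analysis: "The baseline demographic and lesion characteristics and angiographic and clinical outcomes will be evaluated by descriptive statistics". It adds "These calculations will be performed under the assumption that the data are in a normal distribution". SAP 7.1 and 7.2 repeat both statements.

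SAP 7.2 goes on to give a rule for each type of variable:
- Continuous: "All continuous variables will be summarised using the following descriptive statistics: n (non-missing sample size), mean and standard deviation".
- Categorical: "The frequency and percentages (based on the non-missing sample size) of observed levels will be reported for all categorical measures".

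The SAP table listing gives the statistics for Table 7 (core-lab lesion data) as "n, mean, SD, Median, min, max, n" (%), so both styles of summary are available for that table. Table 7 opens with CASS Segment, whose shell is N and N missing, mean ± SD, minimum and maximum, and median (IQR). The next data row, "Lesion location", is laid out by level: missing, distal, mid, ostial, proximal. Table 6 (site-reported) has a row "Vessel treated", also by level, with bypass graft as one level.

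**The concern.** A segment code names a place. Its numerical value carries no quantity, so a mean, SD, median or IQR of the codes describes the numbering and not the lesions. Followed as written, the row yields figures that nobody can interpret.

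What is at stake is one item of description. The objective covers native coronary arteries and bypass grafts, and the protocol sends angiograms to an independent core laboratory. A reader may reasonably want to see, from that laboratory, which vessels or segments were treated. In the planned tables the CASS row is the only core-lab row that could show this, and its format prevents it.

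**Working it through.** The plan states no figure to reproduce. The check compares the passages and then illustrates the point numerically.

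**1. Is the field categorical?** The documents do not define CASS Segment, and it is absent from the SAP abbreviation list. Its name denotes a part of something, it carries no unit (lesion length and MLD are in mm), and it stands directly above the lesion-location row. I take it to be a nominal code. This is an assumption.

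**2. Does the shell follow SAP 7.2?** Under that assumption SAP 7.2 requires counts and percentages by level. The shell has none. Other coded or graded core-lab items in Table 7 do follow the rule: pre-procedure TIMI grade (0, 1, 2, 3), eccentricity, thrombus, calcification, bifurcation. CASS Segment is the exception.

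**3. Does another core-lab row supply the information?** The lesion-location row gives position within a vessel but not which vessel: a mid lesion may lie in the LAD, the LCx or the RCA. The bifurcation rows do not name the vessel either. Table 7 has no other vessel or segment row.

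**4. What would the row report?** The number of lesions and their distribution are not given, so assume 60 lesions at three sites A, B and C, split 30, 20 and 10. With codes a, b and c:

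mean = (30a + 20b + 10c) / 60

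SD = √{[30a² + 20b² + 10c² − 60 × mean²] / 59}

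| Codes for A, B, C | Mean | SD | Median | n (%) at A, B, C |
|---|---|---|---|---|
| 1, 2, 3 | 100/60 = 1.67 | 0.75 | 1.5 | 30 (50.0), 20 (33.3), 10 (16.7) |
| 2, 12, 18 | 480/60 = 8.00 | 6.38 | 7.0 | the same |
| 18, 2, 12 | 700/60 = 11.67 | 7.22 | 15.0 | the same |

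The lesions are identical in all three lines and only the labels differ. The median moves as much as the mean, so printing it beside the mean does not rescue the row.

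The reverse also holds: different lesions can give the same mean. Thirty lesions coded 1 and 30 coded 13 give (30 × 1 + 30 × 13)/60 = 7.0, with SD √(60 × 6²/59) = 6.05. Sixty lesions all coded 7 also give a mean of 7.0, with SD 0. The first set has no lesion in segment 7.

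**The case against.** The strongest reply is that this is one misclassified row in a mock table, in a study that plans no hypothesis test and no confidence interval. The row is a baseline descriptor. It enters neither the primary endpoint nor any secondary endpoint. The vessel treated, including bypass graft, is already tabulated from site data in Table 6, and the documents nowhere require core-lab confirmation of the vessel. The segment values also stay in the data set and can be tabulated at any time. All of this stands, and it limits the point to a minor correction. It does not justify the row: SAP 7.2 calls for counts, and the shell does not provide them.

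Three stronger readings are tempting, and the documents do not support them.

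- *The normality sentence forces means onto categorical data.* It is worded without exception, and yes/no items and TIMI grades cannot be normal. But SAP 7.2 confines mean and SD to continuous variables. Tables 1, 2 and 9 are n (%), and TIMI grade, dissection and perforation are shown by level. The CASS row contradicts the SAP's rule and does not follow from protocol section 9.
- *The sentence distorts the results for continuous measures.* A mean and SD need no normality, no inference is planned, and the continuous shells also carry the median, IQR, minimum and maximum.
- *The core-lab record of lesion site is lost altogether.* Position within the vessel is tabulated by category in the same table. What is missing is narrower: a readable core-lab count by vessel or segment.

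**Conclusion.** Wrong as written (minor). If CASS Segment is a nominal code, its shell in SAP Table 7 contradicts SAP 7.2 and yields figures that depend on the numbering of the segments. As a result, the core-lab distribution of treated segments cannot be interpreted from the planned tables. No endpoint, sample size or other reported result is affected, and the site-reported vessel remains available.

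The conclusion rests on reading the field as a location code, which the documents suggest but do not state. The figures in the illustration use assumed codes and an assumed split of lesions; they show the mechanism and are not a forecast for this trial. The normality sentence is loosely worded, but it is not the cause and changing it would alter no result.

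**What to change.** In SAP Table 7, replace the CASS Segment shell with n (%) per segment, naming each segment, plus a missing level as elsewhere in the table. If the counts per segment would be sparse, group them by the vessel derived from the segment. Show bypass grafts separately where the coding identifies them; the documents do not say whether it does. State in the SAP what the code is.

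The cost is one table row, which becomes somewhat longer. No new data are needed, and nothing changes in the endpoints, the sample size or the study procedures.

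Two changes are optional tidying. The normality sentence could be dropped from protocol section 9 and SAP 7.1 and 7.2. The SAP 7.2 list for continuous variables (n, mean and SD) could be extended to the median, IQR, minimum and maximum that the shells already show.

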11.1 Selection of Clinical Sites and Investigator

The sponsor will select Investigators who are qualified by training and experience, and are legally entitled to perform clinical research and to participate in the investigation of the study device. Sites will be selected based upon review of a recent site assessment and the qualifications of the Primary Investigator at the site.

11.2 Protocol and Informed Consent Approval

11.2.1 Protocol/Subject Informed Consent Initial Approval

Institutional Review Board (IRB) approval for the protocol, informed consent form and other study related documents will be obtained by the Primary Investigator at each investigational site prior to participation in this trial. The approval letter must be signed by the IRB chairperson or authorized representative prior to the start of this trial and a copy must be provided to the Sponsor. In addition, the Investigator or designee will provide the Sponsor with all required documentation necessary for initial and ongoing study approval at their site.

In accordance with the investigational site IRB requirements, the Investigator will (a) advise the IRB of the progress of this trial on a regular basis until study completion; (b) obtain written IRB approval at predetermined time points to continue the trial; and (c) submit any amendments to the protocol as well as associated informed consent form changes and obtain written IRB approval obtained prior to implementation.

No investigative procedures other than those defined in this protocol will be undertaken on the enrolled subjects without the written agreement of the IRB and Sponsor.

11.2.2 Protocol/Subject Informed Consent Approval of Amendments

If the protocol and/or the subject informed consent need an amendment, the Sponsor is required to submit such amendment to the Regulatory Agencies and/or other regulating body in each participating country for approval. Approved protocol amendments will be provided to the Investigators by the Sponsor prior to implementing the amendment. The Primary Investigator is responsible for notifying the IRB of the protocol amendment (administrative changes) or obtaining IRB approval of the protocol amendment (changes in subject care or safety), according to the instructions provided by the Sponsor with the protocol amendment.

Acknowledgement/approval by the IRB of the protocol amendment must be documented in writing prior to implementation of the protocol amendment. Copies of this documentation must also be provided to the Sponsor.

11.3 Protocol Deviations

It is the Investigator's responsibility to ensure that there are no deviations from the protocol in full compliance with all established procedures of the IRB/MEC/HREC. The Investigator will not deviate from the protocol for any reason except in cases of medical emergencies, when the deviation is necessary to protect the life or physical wellbeing of the subject. All deviations must be reported to the Sponsor. The occurrence of protocol deviations will be monitored by the Sponsor or designee. Investigators will inform their IRB/MEC/HREC of all protocol deviations in accordance with their specific IRB/MEC/HREC reporting policies and procedures.

In the event that an Investigator does not comply with the Investigator Agreement or protocol, the Sponsor will notify the Investigator of the site's non-compliance. Continued non-compliance may result in further escalation in accordance with the Sponsor's SOP.

